## 7.5 SECONDARY ENDPOINT(S)

### 7.5.1 Key secondary endpoint(s)

The key secondary endpoint is change from baseline in trough FEV1 after 4 weeks of treatment.

Analyses will be performed in PIFR optimal ( $\geq 60$  L/min) group and PIFR sub-optimal ( $< 60$  L/min) group separately.

#### 7.5.1.1 Primary analysis of the key secondary endpoint(s)

The key secondary endpoint will be analyzed using the restricted maximum likelihood (REML) based approach using a mixed model with repeated measurements (MMRM). The analysis will be performed on the FAS within the optimal and sub optimal PIFR groups, respectively. The data is collected at baseline (visit 2), visit 3 and visit 4.

The analysis will include the fixed, categorical effect of treatment at each visit and the fixed continuous effect of baseline at each visit. Visits will be treated as repeated measures with an unstructured covariance structure used to model the within-patient measurements.

The Kenward-Roger approximation will be used to estimate denominator degrees of freedom and adjust standard errors. Significance tests will be based on least-squares means using a two-sided  $\alpha = 0.05$  (two-sided 95% confidence intervals).

If a patient misses a visit, the missing data will not be imputed. The mixed effect model will handle missing data based on a likelihood method under the “missing at random” assumption.

The following SAS code will be used for the analysis.

```
PROC MIXED DATA=alldat cl method=reml order=formatted;
  CLASS usubjid trtp (ref=last) tptno;
  MODEL chg = trtp*tptno base*tptno / ddfm=kr solution;
  REPEATED tptno / subject=usubjid type=un r rcorr;
  LSMEANS tptno*trtp / pdiff=all om cl alpha=0.05 slice=tptno;
  RUN;
```

Here tptno is the planned analysis day number for each visit, the endpoint is chg, baseline value of the endpoint is base and the treatment group is trtp.

The data set alldat will be set to the optimal and sub-optimal PIFR subgroups, respectively. The data set should only include post baseline visits since change from baseline will be identical to zero for the baseline visit.

In the event of non-convergence, the following methods will be attempted (in order) to overcome it:

1. Add the ‘singular=1e-10’ option in the model statement – This raises the threshold at which columns are declared linearly dependent (from typically 1e-12).
2. Set ‘maxiter=100’ in the PROC MIXED statement – This increases the number of convergence iterations used from a default of 50.
3. Set ‘scoring=4’ to specify use of the Fisher scoring algorithm in the first 4 iterations.
4. Include the statement ‘performance nothread’ – this removes multi-threading from the calculations.

#### 7.5.1.2 Sensitivity analysis, subgroup analysis, exploratory analysis of the key secondary endpoint(s)

##### **Sensitivity analysis**

Additional models will include covariates such as disease severity (e.g. GOLD stage), gender and age. These models will be analyzed separately for each PIFR subgroup.

##### **Missing data analysis**

A multiple imputation analysis will be performed on the key secondary endpoint similar to that of the primary endpoint described in section 7.4.2.

##### **Homogeneity of treatment effect**

To assess the homogeneity of the treatment effect on the key secondary endpoint across the levels of PIFR subgroups, the same MMRM model as in the key secondary analysis will be fitted in the overall population but replacing the treatment term by a treatment-by-PIFR subgroup term. A descriptive p-value of treatment effect homogeneity at week 4 will be calculated. No overall treatment effect will be estimated from this model as it is not interpretable. The analysis will be done separately for population before and after COVID-19.

Similarly, the same MMRM model as in the key secondary analysis will be fitted in the overall population but replacing the treatment term by a treatment-by-continuous baseline PIFR term. A descriptive p-value of treatment effect homogeneity at week 4 will be calculated. No overall treatment effect will be estimated from this model as it is not interpretable. The analysis will be done separately for population before and after COVID-19.

The results of the analysis of the key secondary endpoints for tiotropium + olodaterol FDC within the optimal and sub-optimal PIFR groups will be presented in a forest plot and the treatment by PIFR subgroup interaction p-value will be provided. Sensitivity analysis will be performed by including additional covariates such as severity, gender and age in the model to adjust for potential differences in prognostic factors between sub-optimal and optimal PIFR subgroups.

### **7.5.2        Other Miscellaneous endpoint(s)**

For the FVC data descriptive statistics at screening are planned for this section of the report.

The analyses will be done separately for each PIFR sub group.

### **7.7        EXTENT OF EXPOSURE**

Extent of exposure will be summarized using descriptive statistics for days of exposure as well as number (%) of patients whose total exposure falls in the categories of <2weeks and 2-<4weeks and more than 4 weeks.

### **7.8        SAFETY ANALYSIS**

All safety analyses will be performed on the treated set.

#### **7.8.1        Adverse Events**

Unless otherwise specified, the analyses of adverse events will be descriptive in nature. All analyses of AEs will be based on the number of subjects with AEs and NOT on the number of AEs.

For analysis multiple AE occurrence data on the CRF will be collapsed into an AE provided that all of the following applies:

- All AE attributes are identical (LLT, intensity, action taken, therapy required, seriousness, reason for seriousness, relationship, outcome)
- The occurrences were time-overlapping or time-adjacent (time-adjacency of 2 occurrences is given if the second occurrence started on the same day or on the day after the end of the first occurrence).

For further details on summarization of AE data, please refer to (13,14).

The analysis of adverse events will be based on the concept of treatment emergent adverse events. That means that all adverse events occurring between first drug intake till last drug intake + residual effect period (21 days) will be assigned to the randomized treatment. All adverse events occurring before first drug intake will be assigned to 'screening' and all adverse events occurring after the residual effect period will be assigned to 'post-treatment' (for listings only). Adverse events that start before first drug intake and deteriorate under treatment will also be considered as 'treatment-emergent'. For details on the treatment definition, see Section 6.1.

According to ICH E3 AEs classified as 'other significant' needs to be reported and will include those non-serious and non-significant adverse events with

- (i) 'action taken = discontinuation' or 'action taken = reduced', or
- (ii) marked haematological and other lab abnormalities or lead to significant concomitant therapy as identified by the Clinical Monitor/Investigator at a Medical Quality Review Meeting.

An overall summary of adverse events will be presented.

The frequency of subjects with adverse events will be summarized by treatment, primary system organ class and preferred term (mention MedDRA levels to be displayed in the tables). Separate tables will be provided for subjects with other significant adverse events according to ICH E3 and for subjects with serious adverse events.

The system organ classes will be sorted alphabetically, preferred terms will be sorted by frequency (within system organ class).

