Based on these observations, marketing authorization for tiotropium + olodaterol (5µg /5µg) FDC (total daily dose) has been granted in US, Canada, Australia, in all European countries within the decentralized procedure as well as in a number of other countries worldwide.

For a more detailed description of the drug profile refer to the current Summary of Product Characteristics (SmPC) for Spiolto® or the United States Prescribing Information (USPI) for Stiolto® which are included in the Investigator Site File (ISF).

Boehringer Ingelheim's Respimat® inhaler will be used for administration of study drug. The medication is provided as an aqueous solution in a cartridge, which is inserted into the device prior to first use. A propellant-free device, the Respimat® inhaler generates a soft mist which is released over a period of approximately 1.5 seconds. The fraction of fine particles accessible to the lungs and airways is very high compared with many metered dose aerosols or dry powder devices. The use of the Respimat® inhaler has been shown to be safe with regards to paradoxical bronchoconstriction during chronic use in patients with COPD ([P05-08465](#)). The Residual Effect Period (REP) of tiotropium + olodaterol FDC is 21 days.

Salbutamol used as rescue medication in this trial is a short-acting, selective beta₂-adrenergic receptor agonist used in the treatment of asthma and COPD. Salbutamol is a bronchodilator that opens up the airways affected by bronchoconstriction, therefore relieving the wheezing and shortness of breath. Salbutamol can be used as a fast-acting rescue medication that provides quick relief..

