washout period. Once randomized, patients will receive either tiotropium + olodaterol FDC via Respimat® inhaler or matching placebo. All patients will receive salbutamol for use as rescue medication, as needed, from screening visit until EOT. At the conclusion of EOT visit, patients can resume taking their regular COPD medications. At the EOT visit, investigator should advise the patients on appropriate care during the follow-up period and after completion of the study. During the follow-up period, patients will not receive study medication. Rescue medication will not be dispensed at EOT visit for use during the follow-up period. Patients on ICS maintenance therapy (monotherapy or combination with bronchodilators) will not be eligible to participate in this study.

Body plethysmography measurements will be an optional trial procedure at visit 2 and will be done only at selected sites on selected patients. Approximately 30 (15%) patients are expected to participate in this procedure. Patients participating in this optional trial procedure will have to sign a separate informed consent. At the screening visit, an assessment will be completed to see if the patient can perform technically acceptable body plethysmography measurements.

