4.2.3 Restrictions

4.2.3.1 Restrictions regarding concomitant treatment

Table 4.2.3.1: 1 Overview of permitted and restricted medication

Drug Class	Sub-class	Prior to study	Study Period		
			Screening Period	Treatment Period	Follow-up Period
Corticosteroids	Inhaled corticosteroids	Permitted ¹	NOT permitted	NOT permitted	Permitted
	Oral corticosteroids	Permitted ²	NOT permitted	NOT permitted	Permitted
	Injected Corticosteroids – local administration (for treatment of e.g. bursitis)	Permitted	Permitted	Permitted	Permitted
β-adrenergics	Inhaled short-acting β-adrenergics	Permitted	Rescue ³	Rescue ³	Permitted
	Inhaled long-acting β-adrenergics (e.g. formoterol / salmeterol)	Permitted	Permitted ⁴	NOT permitted	Permitted
Anti-cholinergics	Short-acting anticholinergics (inhalation aerosol, nasal spray)	Permitted	Permitted ³	NOT permitted	Permitted
	Long-acting anticholinergics (i.e. tiotropium, aclidinium, glycopyrronium, umeclidinium, tiotropium + olodaterol)	Permitted	Permitted ⁴	NOT permitted	Permitted
Combinations	ICS/LABA	Permitted ¹	NOT permitted	NOT permitted	Permitted
	ICS/SABA	Permitted ¹	NOT permitted	NOT permitted	Permitted

Table 4.2.3.1: 1 Overview of permitted and restricted medications (cont.)

Drug Class	Sub-class	Prior to study	Study Period		
			Screening Period	Treatment Period	Follow-up Period
Combinations	short-acting anticholinergic/ SABA	Permitted	Permitted ³	NOT permitted	Permitted
	Long-acting anticholinergics/long-acting β -adrenergics (e.g. glycopyrronium+indacaterol, umeclidinium+vilanterol)	Permitted	Permitted ⁴	NOT permitted	Permitted
	ICS, long-acting anticholinergics, long-acting β -adrenergics, (e.g. fluticasone+umeclidinium, vilanterol)	Permitted ¹	NOT permitted	NOT permitted	NOT permitted
Miscellaneous	Other investigational drugs (1 month or 6 half-lives (whichever is greater) prior to V1)	Permitted	NOT permitted	NOT permitted	NOT permitted
	Cromolyn sodium / nedocromil sodium (if prescribed for non-asthma condition)	Permitted	Permitted	Permitted	Permitted
	Antihistamines, antileukotrienes (if prescribed for non-asthma condition)	Permitted	Permitted	Permitted	Permitted
	Methylxanthines (if prescribed for non-asthma condition)	Permitted	Permitted	Permitted	Permitted
	Mucolytics (not containing bronchodilators; stabilized 6 wks. prior to V1)	Permitted	Permitted	Permitted	Permitted
	Phosphodiesterase type 4 (PDE-4) inhibitor (e.g. roflumilast)	Permitted ⁵	NOT permitted	NOT permitted	NOT permitted

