7.3.4 Safety analyses

Adverse events will be coded using the Medical Dictionary for Regulatory Activities (MedDRA) coding dictionary. Standard BI summary tables and listings will be produced. All adverse events with an onset between start of treatment and end of the REP, a period of 21 days after the last dose of trial medication, will be assigned to the treatment period for evaluation. All randomized patients who have taken at least one dose of study drug (i.e., the

treated set) will be included in the safety analysis. In general, safety analyses will be descriptive in nature and will be based on BI standards. No hypothesis testing is planned.

Statistical analysis and reporting of adverse events will concentrate on treatment-emergent adverse events. To this end, all adverse events occurring between start of treatment and end of the residual effect period will be considered 'treatment-emergent'. The residual effect period is defined as 21 days. Adverse events that start before first drug intake and deteriorate under treatment will also be considered as 'treatment-emergent'.

Frequency, severity, and causal relationship of adverse events will be tabulated by system organ class and preferred term after coding according to the current version of MedDRA.

All treated patients will be included in the safety analysis. In general, safety analyses will be descriptive in nature and will be based on BI standards. No hypothesis testing is planned.

Laboratory data will be analysed both quantitatively as well as qualitatively. The latter will be done via comparison of laboratory data to their reference ranges. Values outside the reference range as well as values defined as clinically relevant will be summarized.

Treatment groups will be compared descriptively with regard to distribution parameters as well as with regard to frequency and percentage of patients with abnormal values or clinically relevant abnormal values.

Vital signs, physical examinations, or other safety-relevant data observed at screening, baseline, during the course of the trial and at the end-of-trial evaluation will be assessed with regard to possible changes compared to findings before start of treatment.

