### 7.2 CONCOMITANT DISEASES AND MEDICATION

Only descriptive statistics are planned for this section of the report. A table of number (%) of patients with concomitant diagnoses (CDs) by system organ class (SOC) and preferred term (PT) will be included along with a supporting listing. Concomitant diagnoses will be coded with the most recent version of the Medical Dictionary for Regulatory Activities (MedDRA) in effect at database lock.

Frequency tables (%) will be presented for medical history and COPD background characteristics.

Pulmonary medication will be summarized as the number (%) of patients taking pulmonary medications within the last three months before visit 1 and during the treatment periods.

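### The 21-day residual-effect window for adverse events coincides with the follow-up in which patients may resume LAMA/LABA drugs, and the SAP text specifies no display that separates the two

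*SAP*

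**What the plan says.** **Attribution.** SAP 7.8.1 assigns every AE from first drug intake "till last drug intake + residual effect period (21 days) will be assigned to the randomized treatment". Protocol 7.3.4 has the same rule: onset up to the end of the residual effect period, "a period of 21 days after the last dose of trial medication, will be assigned to the treatment period for evaluation". SAP 7 analyses safety by planned arm, so the window applies equally to active and placebo.

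**Origin of the 21 days.** Protocol 1.2 gives it as a property of the active product: "The Residual Effect Period (REP) of tiotropium + olodaterol FDC is 21 days".

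**Resumed therapy.** Protocol 3.1 says: "At the conclusion of EOT visit, patients can resume taking their regular COPD medications". In Table 4.2.3.1:1 the follow-up column reads Permitted for inhaled LABA, for the LAMA row ("Long-acting anticholinergics (i.e. tiotropium, aclidinium, glycopyrronium, umeclidinium, tiotropium + olodaterol") and for the combination row ("Long-acting anticholinergics/long-acting β -adrenergics (e.g. glycopyrronium+indacaterol, umeclidinium+vilanterol").

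**What is displayed.** SAP 7.8.1 plans an overall AE summary, tables by system organ class and preferred term, and tables of serious and other significant AEs. All count subjects, not events. SAP 7.2 summarises pulmonary medication taken "within the last three months before visit 1 and during the treatment periods".

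**The concern.** A residual-effect window rests on the idea that what happens shortly after the last dose can still be ascribed to the randomised treatment. That is less clear when patients in either arm may be taking open-label drugs of the same class in that time. A placebo patient who restarts tiotropium + olodaterol on Day 30 and has an AE on Day 40 is counted under placebo.

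The tables affected are the only AE tables by arm that the SAP text specifies, and SAP 7.8.2 to 7.8.4 route clinically relevant laboratory, vital-sign and ECG findings into them. If resumption is common, a real difference between active and placebo would look smaller than it was during randomised treatment, and a reader could not tell from the planned output how far this had happened.

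**Working it through.** **1. Do the two periods coincide?** By the Protocol flow chart, trial medication is given in the clinic at Visit 4 (Day 29) and the follow-up call is on Day 50. 50 − 29 = 21 days, which reproduces the stated residual effect period. Regular medication may restart at the end of Visit 4, so both periods are Days 30 to 50.

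**2. Share of the window after the last dose.** Completer: 21 / (29 + 21) = 21/50 = 42%. A patient whose last dose is on Day 15: 21 / (15 + 21) = 21/36 = 58%.

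**3. Effect on a rate ratio.** The documents give neither AE rates nor the share who resume, so both are assumed. Let *r* be the true on-drug to off-drug rate ratio, *f* the share in each arm on a study-class drug throughout the 21 days, and the off-drug rate 1 per day.

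- Placebo: 29 + 21·*f*·*r* + 21·(1 − *f*)
- Active, effect ends at last dose: 29·*r* + 21·*f*·*r* + 21·(1 − *f*)
- Active, residual effect lasts all 21 days: 50·*r* (residual plus resumed drug taken as no more than *r*)

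| *r* | *f* | No residual effect | Full 21-day residual effect |
|---|---|---|---|
| 2.0 | 0 | 79/50 = 1.58 | 100/50 = 2.00 |
| 2.0 | 0.5 | 89.5/60.5 = 1.48 | 100/60.5 = 1.65 |
| 2.0 | 1 | 100/71 = 1.41 | 100/71 = 1.41 |
| 1.5 | 0 | 64.5/50 = 1.29 | 75/50 = 1.50 |
| 1.5 | 0.5 | 69.75/55.25 = 1.26 | 75/55.25 = 1.36 |
| 1.5 | 1 | 75/60.5 = 1.24 | 75/60.5 = 1.24 |

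**4. The same check on subjects with an AE, which is what will be tabulated.** Assume 29-day risks of 20% on drug and 10% off drug with constant hazards, so the on-treatment ratio is 2.00.

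- Placebo: 1 − 0.9·[*f*·0.8^(21/29) + (1 − *f*)·0.9^(21/29)] = 16.6%, 20.0% and 23.4% at *f* = 0, 0.5 and 1
- Active, no residual effect (0.8 replaces the leading 0.9): 25.9%, 28.9% and 31.9%; ratios 1.56, 1.44 and 1.36
- Active, full residual effect: 1 − 0.8^(50/29) = 31.9% at every *f*; ratios 31.9/16.6 = 1.92, 31.9/20.0 = 1.60 and 31.9/23.4 = 1.36

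The direction agrees with step 3. Resumption alone moves the placebo proportion from 16.6% to 23.4%.

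**5. How much is due to resumption?** Compare *f* = 0 with *f* = 1 for *r* = 2. With no residual effect, the extra 21 off-drug days already take the ratio from 2.0 to 1.58, and resumption takes it on to 1.41. With a full residual effect, the whole fall from 2.0 to 1.41 is resumption.

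**The case against.** The case against has several sound parts.

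- **Causality is tabulated.** Protocol 7.3.4 tabulates causal relationship, and Protocol 5.2.6.1.6 asks investigators to weigh concomitant medication. To say that nothing separates these events would go too far. The separation is only partial: the investigator is blinded and, where the resumed drug is of the study class, an event typical of that class fits either source.
- **Internal standards are cited.** SAP 7.8.1 refers to a company standard for AE summaries that is not in the documents. What can be said is that the SAP text specifies no separating display, not that none will be produced.
- **SAP 7.2 is ambiguous.** A reader might infer that medication in follow-up is never summarised. The SAP does not define where the treatment periods end, and Protocol 7.3.4 counts the 21 days as treatment period for AEs. If that definition carries over, resumed use is covered but pooled with on-treatment use. Either way it is not shown separately.
- **The other-significant-AE table is little exposed.** After a completer's last dose there is no trial drug left to stop or reduce, and scheduled laboratory tests end at Visit 4. Only the limb on significant concomitant therapy is open.
- **Resumption is allowed, not required.** No inclusion criterion demands earlier LAMA or LABA use, so full uptake is the extreme case. Some uptake is plausible: Protocol 1.4.2 keeps patients on prescribed treatment until three days before randomisation, and Protocol 6.2.3 uses the follow-up call to advise continuing regular COPD medication.
- **The window is legitimate.** It is pre-specified, the same in both documents, and tied to the drug's stated residual period.

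These points narrow the concern. They do not remove the overlap between the attribution rule and permitted resumption.

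**Conclusion.** The point holds in a limited form. As written, the rule can tabulate under placebo an AE that arises on resumed study-class drug, and the SAP text offers only the causality table to tell such events apart. For a completer, 42% of the AE window is open to this.

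The size is conditional on assumed uptake, AE rates and duration of residual effect. For a true ratio of 2.0, the tabulated contrast could lie anywhere from 1.41 (all resume) to 2.0 (nobody resumes, full residual effect).

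Three stronger readings are not supported:

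- **That drug AEs will in fact be counted as placebo AEs to a known extent.** The documents do not give uptake.
- **That the fall in the ratio is all due to resumption.** If the effect stops at the last dose, most of it comes from adding 21 off-drug days.
- **That the safety comparison should rest only on a window ending at the last dose.** That would leave out AEs within the residual period that Protocol 1.2 states for the combination.

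Protocol 5.2 says there are no safety endpoints, and Protocol 7.3.4 plans no hypothesis tests for safety. No efficacy result, power figure or error rate is affected. This is a low-cost improvement to a descriptive analysis.

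**What to change.** - **SAP 7.8.1:** keep the residual-effect-period tables as planned. Add supplementary AE and SAE tables by arm restricted to onset from first dose to last dose + 1 day. The alternative is to restrict them to the earlier of last dose + 21 days and restart of a LAMA/LABA, which keeps more of the residual period but relies on recorded restart dates. State that the two sets are read together for the between-arm description and that neither replaces the other.
- **SAP 7.2:** say where the treatment periods end, and summarise pulmonary medication resumed in follow-up separately by arm.

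**Cost:** SAP wording and a few more table runs. No new data are needed: AEs are collected to the end of follow-up (Protocol 5.2.6.2.1) and concomitant therapy is recorded at the follow-up visit (Protocol 6.2.3). The drawback is that late residual-effect AEs appear only in the existing tables if the last-dose cut is used. No change to which medication patients may take is implied.
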